## **8.0. MEASUREMENTS, EVALUATIONS, AND ANALYTICAL METHODS**

Assessments are conducted at five time points: 1) screening for study enrollment, 2) baseline assessment, 3) post intervention assessment, 4) three month follow up, 5) six month follow up. Measurement tools are described in the section that follows. In Table 3, at the end of the section, the schedule for instrument administration is provided. The post intervention assessment is limited to the measures where it is hypothesized the intervention may have an immediate measurable effect. Participants will be informed and assured that data collected from research assessments will not be shared with treatment staff. Prior research has indicated substance abusers are more likely to self disclose substance use behaviors when there are not legal or clinical contingencies tied to their self report.

A major consideration in planning treatment outcome research involves formulation of an effective plan to ensure follow-up data are obtained. To encourage participation in follow-up, the length of each visit has been kept relatively short. Participants will be paid in cash or vouchers for completion of follow-up assessments. Reasonable and non-coercive reimbursement sums will be determined on a site-by-site basis. It is anticipated that follow up rates for participants while they are still in treatment will be extremely high. Participants who have left the area will be interviewed by phone. A paper/pencil version of the Sexual Behavior Inventory (usually administered via ACASI) will be created so that we can collect data on participants who have left the area or are otherwise unable to be interviewed in person. All participants will complete a locator sheet that identifies stable individuals who are likely to know of the participants' whereabouts in the future. In a previous treatment outcome study conducted in a methadone clinic by the lead investigator the six month follow up completion rate was 91% using similar methods (Calsyn et al. 1994). To obtain a follow up estimate for the ODF sample we turned to the NIDA Collaborative Cocaine Treatment Study where 85.2% of participants completed the 5 or 6 month follow up.

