where  $\varepsilon_k = (\varepsilon_{11k}, \dots, \varepsilon_{I(2m)k})'$  has a multivariate normal distribution with mean zero and covariance matrix  $\sigma^2 R$ . Here the correlation matrix  $R$  contains 1 for its diagonal entries and  $\rho$  for off-diagonal entries. Here  $\sigma^2$  is the variance of  $\varepsilon_{ijk}$  and  $\rho$  represents the correlation between any two observations from the same cohort as well as the correlation between two observations from different cohorts within the same CTP site. Note that we assume that the correlation between two observations from the same cohort is the same as the one between two observations from different cohorts within the same CTP site. Under this linear model, to detect the effect size  $\Delta$  in the average number of unprotected vaginal and anal intercourse between the intervention and control conditions at the type I error  $\alpha$  with a power of  $1-\beta$ , we need the following number of cohorts per condition in the study:

$$m = 2(z_{1-\alpha/2} + z_{1-\beta})^2 \{1 + (I-1) * \rho\} / (I * (\Delta)^2),$$

where  $z_{1-\beta}$  is the  $(1-\beta)$ th percentile of the standard normal distribution. This formula is the same as Formula (5.1) in Donner and Klar (2000).

From the above formula, we see that to calculate a required sample size we need to determine the standardized effect size  $\Delta$ . We have estimated the effect size on the basis of clinically important intervention effects observed in prior studies. The NIMH Multisite HIV Prevention Trial Group (1998) used the number of unprotected vaginal and anal intercourse acts as a primary outcome measure in Project Light. They observed an effect size ( $\Delta$ ) of 0.29. Assuming that we have an intracluster correlation no greater than  $\rho$  of 0.01 and an average of 8 participants per cohort ( $I=8$ ), using the above formula we find that the number of cohorts per condition required to detect the effect size of 0.29 with a type I error rate of 0.05 and a power of 80% is:

$$m = 2 * (1.96 + 0.84)^2 * \{1 + (8-1) * 0.01\} / (8 * (0.29)^2) = 25,$$

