Since all covariates used in the model are baseline covariates, we can assume we have complete information on the covariates. A patient who drops out during the study will result in missing outcomes. To be able to deal with possible missing-data, we will use the multiple imputation technique combined with the standard Generalized Estimating Equation (GEE) method for the parameters in model (1),  $\beta = (\beta_0, \beta_1, \beta_2, \beta_3, \beta_4)$ . A similar method for handling missing covariates has also been proposed by Xie and Paik (1997). In this multiple imputation approach, a missing value of the outcome will be imputed using a Bayesian bootstrap method (Rubin, 1987; Xie and Paik, 1997) to obtain 5 imputed values, resulting in 5 complete-data sets. We will use the following steps in this multiple imputation scheme: (1) we will build a logistic regression model to predict the missingness for the outcome; (2) based on this model we will assign a propensity score for missingness for each case; (3) for each patient with a missing outcome (Y), its donor pool of patients having observed outcomes will

be found such that their assigned propensity scores are close to the assigned propensity score for the patient with the missing outcome; (4) for the missing value of Y for the patient, we will generate 5 imputation values from its donor pool according to the Approximate Bayesian Method (Rubin, 1987).

This multiple imputation method has been implemented by Solas (Statistical Solutions Ltd, 2001). For each complete-data set, we will apply the standard GEE method to get a pair of GEE estimates for  $\beta$  and its variance, resulting in 5 pairs. Then, according to Rubin's formula (Rubin, 1987), we will obtain the multiple-imputation estimate for  $\beta$  and its variance with associated p-value and 95% confidence interval.

Although the above method can handle both missing at random (MAR) and non-MAR missing data patterns, the validity of the method requires appropriately modeling the missing-data mechanism. To assess sensitivity of the conclusions on the assumed missing-data mechanism we will use both a parametric model (Robins et al, 1994; Scharfstein et al, 1999) and a non-parametric model (Wang et al, 1997).

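### Section 11.6 fixes the primary analysis at five imputations, which is valid but leaves avoidable Monte Carlo noise in the p-value and confidence interval

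*Protocol*

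**What the plan says.** Section 11.6 handles missing outcomes in the primary analysis by multiple imputation combined with GEE. A logistic model gives each man a propensity score for missingness, and men with observed outcomes and similar scores form a donor pool. For each missing count, "we will generate 5 imputation values from its donor pool according to the Approximate Bayesian Method". The number also appears where the approach is introduced: "to obtain 5 imputed values, resulting in 5 complete-data sets". Each completed data set gets a standard GEE fit, and "according to Rubin's formula (Rubin, 1987), we will obtain the multiple-imputation estimate" with its variance, p-value and 95% interval. Section 11.7 uses the same multiple-imputation GEE method for the secondary outcomes.

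The protocol gives no reason for the number five. The sensitivity analyses at the end of section 11.6 vary the model for the missing-data mechanism, not the number of imputations.

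Missing outcomes are expected. Section 11.3 allows for 10% attrition. Section 8.0 cites 91% six-month completion in an earlier methadone-clinic study and, as the guide for the drug-free outpatient sample, a cocaine treatment study in which "85.2% of participants completed the 5 or 6 month follow up".

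**The concern.** The imputed counts are random draws, so the pooled estimate and its standard error both carry Monte Carlo error. With five data sets the between-imputation variance is estimated on only four degrees of freedom, so the standard error is noisy as well as the estimate. The usual reassurance is relative efficiency, which is high here. But relative efficiency describes the variance of the estimate over repeated trials. It does not say whether the same locked data, analysed again as prespecified, would give the same verdict.

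At stake is the reproducibility of the primary p-value and interval when the result lies near 0.05, plus a small loss of power. Because the protocol writes the number five into the primary analysis, this is a stated choice and not a detail left open.

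**Working it through.** **Inputs.** From section 11.6: M = 5 and pooling by Rubin's rules. From section 11.3: effect size 0.29, two-sided alpha 0.05, power 80%, intracluster correlation 0.01, "an average of 8 participants per cohort", 10% attrition and 560 enrolled. From section 8.0: 91% and 85.2% completion, so 9% and 14.8% missing. **Assumed:** a fraction of missing information (FMI) of 0.09 to 0.148, close to the missing fraction. A simplified linear-model simulation of donor-pool imputation with 560 men gave FMI 0.09 to 0.19 for 9% to 14.8% missing, so the assumption is reasonable but could be somewhat low.

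**The plan's own figure.** 2(1.96 + 0.84)² × {1 + 7 × 0.01} / (8 × 0.29²) = 24.94, so 25 cohorts and 200 men per condition. This reproduces the protocol. With 560 enrolled in equal arms and 10% lost, 280 × 0.9 = 252 per arm remain. Then 0.29 × √(252 / (2 × 1.07)) − 1.96 = 1.187, which is 88.2% power.

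**Relative efficiency, 1/(1 + FMI/M).** At M = 5 it is 0.982 (FMI 0.09) and 0.971 (FMI 0.148). At M = 50 it is 0.998 and 0.997.

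**Seed SD of Z near 1.96.** Two parts combine, on a scale where the limiting variance is 1:
- noise in the estimate: √(FMI/M);
- noise in the standard error: about 1.96 × ½ × (1 + 1/M) × FMI × √(2/(M − 1)).

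At M = 5 and FMI 0.09 these are 0.134 and 0.075, giving √(0.134² + 0.075²) = 0.15. At FMI 0.148 they are 0.172 and 0.123, giving 0.21. At M = 50 the totals are 0.046 and 0.062. Counting only the first part gives 0.13 to 0.17 at M = 5, which understates the noise.

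**Simulation.** The data are held fixed at a given limiting result and only the imputations are redrawn (200,000 draws). Pooling uses Rubin's reference distribution, df = (M − 1)(1 + 1/r)² with r = (1 + 1/M)FMI/(1 − FMI). At M = 5 this gives df 355 and 134. For the last row the limiting Z itself varies over trials with 80% or 88.2% power. Each cell runs from FMI 0.09 to FMI 0.148. The last row also spans the two power levels.

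| Quantity | M = 5 | M = 20 | M = 50 |
|---|---|---|---|
| Seed SD of Z | 0.15 to 0.20 | 0.07 to 0.10 | 0.05 to 0.06 |
| Limiting p 0.05: 95% range of reported p, FMI 0.09 | 0.026–0.102 | 0.036–0.070 | 0.041–0.062 |
| Same, FMI 0.148 | 0.020–0.129 | 0.032–0.079 | 0.038–0.067 |
| Limiting p 0.03: two seeds disagree on p < 0.05 | 21% to 34% | 0.7% to 4.9% | about 0.1% or less |
| Limiting p 0.08: two seeds disagree | 12% to 20% | 0.3% to 2.6% | below 0.1% |
| Averaged over trials: two seeds disagree | 4% to 7% | 2% to 3% | 1% to 2% |

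**Power.** This uses a noncentral t with the same df and noncentrality divided by √(1 + FMI/M). At 80% limiting power, M = 5 gives 79.1% (FMI 0.09) and 78.3% (FMI 0.148), a loss of 0.9 to 1.7 points. Simulating with an estimated between-imputation variance gives losses of about 1 to 2 points. At 88.2% limiting power, M = 5 gives 87.5% and 86.8%, a loss of 0.7 to 1.4 points.

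**Sensitivity to the assumption.** At FMI 0.20 and M = 5, the 95% range of reported p for a limiting p of 0.05 widens to 0.016–0.155. The power loss at 80% design power is then about 2.5 points.

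**The case against.** The strongest reply is that nothing here is an error. Rubin's variance and reference distribution allow for a finite number of imputations, relative efficiency is at least 0.97, and 560 enrolled against 400 required leaves ample power. All of that stands. A reader might infer that five imputations bias the estimate, inflate the type I error or leave the trial underpowered. The documents support none of these: the pooling rule in section 11.6 is the correct one, and power stays near 87% at the planned enrolment. A loss as large as 3 points would need an FMI of about 0.22 or more, above what the protocol's follow-up figures suggest.

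A second reply is that the most striking case survives the change. At a limiting p of exactly 0.05, two seeds disagree about half the time at any finite number, and the M = 50 range still straddles 0.05. This also stands. The gain lies at values such as 0.03 or 0.08, where disagreement nearly vanishes.

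A third reply is that a statistical analysis plan, not shown, may fix the seed. That would make the result repeatable, but the verdict would still depend on which seed was chosen. Absence of a seed from the protocol is not part of this point.

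Finally, section 11.6 names a particular software package, and the documents do not show how many imputations it can produce. That is a fair practical caution.

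**Conclusion.** The point holds as a low-cost improvement, not as a flaw in validity. Five imputations give an unbiased, properly pooled analysis with more Monte Carlo noise than necessary. Under the assumed FMI, the reported p-value for a borderline result can vary by a factor of about four to six between seeds (0.026 to 0.102, or 0.020 to 0.129). A moderately clear result at p = 0.03 can change verdict in a fifth to a third of seed pairs. Over all trials the effect is modest, at 4% to 7% disagreement against 1% to 2%, and the power cost is 1 to 2 points with no threat to the 80% target.

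These sizes rest on the assumed FMI, equal arms and the protocol's design values. A higher FMI would enlarge them.

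**What to change.** In section 11.6, replace 5 with a larger number such as 50 wherever it appears (imputed values, completed data sets and pairs of estimates). State in section 11.7 that the secondary outcomes use the same number. Rubin's pooling stays as written. Fifty is a convenient choice, not a derived threshold: twenty already removes much of the noise, and fifty brings disagreement at a limiting p of 0.03 down to about 0.1% or less.

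The cost is computing time and confirming that the chosen software can produce that many imputations. No participants, visits or data are affected. The change narrows the zone in which the verdict depends on the seed, but no finite number of imputations removes it.

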### 11.7 Analysis of Secondary Outcomes

There are seven secondary outcomes: number of sexual partners, frequency of "outer course," a dichotomous measure of whether or not the subject is possessing condoms; dichotomous measure of whether the subject reports to have taken or not taken (male and female) condoms from open clinic supplies; attitudes towards condom use as measured by the Condom Barriers Scale; frequency of combining sexual behavior and drug use; and gender role beliefs as measured by the BSRI. All analyses will be performed using an ITT consisting of all randomized participants.

For the continuous-scale outcomes, we will use the same models and estimation methods as used for the analysis of the primary outcome.

For the dichotomous outcomes, we will use marginal logistic regression models (Diggle et al., 1994, p. 147-153). Let  $W_{ijkt}$  be a dichotomous secondary outcome of the  $i$ th subject in the  $j$ th cohort of the  $k$ th participating CTP site at the  $t^{\text{th}}$  follow-up time. Let  $z_{1ijk}$ ,  $z_{2ijk}$ ,  $z_{3ijk}$  and  $z_{4ijk}$  be the same four covariates as defined previously. We will use the following marginal logistic regression for  $W_{ijkt}$ :

$$\log \frac{P(W_{ijkt} = 1)}{P(W_{ijkt} = 0)} = \beta_0 + \beta_1 z_{1ijk} + \beta_2 t + \beta_3 z_{1ijk} * t + \gamma_1 z_{2ijk} + \gamma_2 z_{3ijk} + \gamma_3 z_{4ijk} \quad (1),$$

Similar to the estimation in the analysis of the primary outcome, we will use the multiple imputation GEE method to make inferences about the parameter of interest.

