### **8.3.6. Condom Barriers Scale**

The Condom Barriers Scale (St. Lawrence, Chapdelaine, Devieux et al., 1999) is a 29-item scale with demonstrated reliability and validity. Items are responded to on a 5 point Likert scale from strongly agree to strongly disagree. There are four scales derived from factor analysis; access/availability, partner barriers, effect on sexual experience, and motivational barriers.

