### **11.2 Primary Outcome and Statistical Hypotheses**

There is one primary outcome measure, the number of unprotected vaginal and anal intercourse acts during the three month and six month follow up periods. This measure was used in Project Light (NIMH Multisite HIV Prevention Trial Group, 1998). The primary analyses will test the hypothesis that compared to single-session HIV/AIDS education participants, REMAS participants will significantly decrease their involvement in unprotected vaginal and anal intercourse from baseline assessment to follow up assessments. Intervention effects of secondary efficacy measures of interest will also be tested. We hypothesize that compared to the control group, the experimental group will have fewer sexual partners, engage in more “outer course,” demonstrate an increase in frequency of possessing condoms, in the likelihood of taking condoms from clinic stocks, positive attitude toward condom use, and egalitarian sex role beliefs; and a decrease in the percentage of sexual events that include drug taking.

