To test this hypothesis, we let  $Y_{ijk}$  be the frequency of unprotected vaginal and anal intercourse of the  $i$ th subject in the  $j$ th cohort of the  $k$ th CTP site measured at the  $t^{\text{th}}$  follow-up time. Let  $z_{1ijk}$  be the treatment assignment indicator for the  $i$ th subject in the  $j$ th cohort of the  $k$ th CTP site. Here  $m$  is the number of cohorts per condition within the CTP site. To adjust for the possible imbalance between conditions on the baseline value, we include the baseline value as a covariate; let  $z_{2ijk}$  be the baseline frequency of unprotected vaginal and anal intercourse of the  $i$ th subject in the  $j$ th cohort of the  $k$ th CTP site. The other two covariates we plan to include in the model are (1)  $z_{3ijk}$ , a binary indicator on whether the  $i$ th subject in the  $j$ th cohort of the  $k$ th CTP site is non-monogamous in the six months prior to the baseline and (2)  $z_{4ijk}$ , years of stimulant use for the  $i$ th subject in the  $j$ th cohort of the  $k$ th CTP site. As noted by Sen (1997), analyzing change from baseline does not remove the baseline imbalance. Hence, we propose to model the absolute frequency at a particular follow-up time and include the baseline frequency value as a covariate in regression.

The following marginal model for outcome of count will be used to test this hypothesis:

$$(1) \quad \log E(Y_{ijk}) = \beta_0 + \beta_1 z_{1ijk} + \beta_2 t + \beta_3 z_{1ijk} * t + \gamma_1 z_{2ijk} + \gamma_2 z_{3ijk} + \gamma_3 z_{4ijk}$$

where  $t=0$  for 3 months post intervention and  $t=1$  for 6 months post-intervention.

Based on the assumed model (1), our main null and alternative hypotheses are governed by the regression parameters  $\beta_1$ ,  $\beta_2$  and  $\beta_3$ . For example,  $\beta_3 \neq 0$  indicates that over time the effects of the two study interventions are different;  $\beta_3=0$  corresponds to no difference in the effectiveness of the interventions over time. If  $\beta_3=0$ , the parameter  $\beta_2$  estimates the rate of change in the outcome measure from 3 to 6 months post-intervention in the two intervention groups, and the parameter  $\beta_1$  estimates the difference between the experimental and control intervention, which is the same at the two follow-up assessment times.

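### Section 11.7 adjusts the two binary secondary outcomes for baseline unprotected intercourse instead of their own baseline, and its same-models rule fixes the covariate and link badly for the scale scores

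*Protocol*

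**What the plan says.** Section 11.6 sets out one model for the primary outcome, introduced as follows: "The following marginal model for outcome of count will be used to test this hypothesis". It is a log-mean model with treatment, time, their interaction, and three baseline covariates, z2 to z4. The reason for z2 is stated: "To adjust for the possible imbalance between conditions on the baseline value, we include the baseline value as a covariate". The same sentence then defines z2 to "be the baseline frequency of unprotected vaginal and anal intercourse of the" subject concerned. z3 is non-monogamy in the six months before baseline and z4 is years of stimulant use.

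Section 11.7 lists seven secondary outcomes and treats them in two groups.

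- Dichotomous (possessing condoms; taking clinic condoms): a marginal logistic model in z1 to z4, which are to "be the same four covariates as defined previously".
- The rest: "For the continuous-scale outcomes, we will use the same models and estimation methods as used for the analysis of the primary outcome".

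The second group includes "attitudes towards condom use as measured by the Condom Barriers Scale", for which 8.3.6 says: "Items are responded to on a 5 point Likert scale from strongly agree to strongly disagree". It also includes the BSRI, which 8.3.7 scores as means from one to seven.

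On combining drugs and sex, the hypothesis in 11.2 is "a decrease in the percentage of sexual events that include drug taking", whereas 11.7 lists a frequency.

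**The concern.** Adjusting a follow-up measure for its own baseline does two things: it corrects for chance differences between arms on that measure, and it removes the between-person variation that baseline predicts. Another outcome's baseline does either only to the extent that the two are correlated. Section 11.6 relies on the first argument for the primary outcome. Section 11.7 keeps the covariate but loses the argument, because frequency of unprotected intercourse is not the baseline value of condom possession.

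This matters because 11.2 words several secondary hypotheses as increases or decreases, yet the models cover only the 3-month (t=0) and 6-month (t=1) assessments. Baseline therefore does not enter as a repeated measure either. Where z2 is the primary outcome's baseline, the secondary outcome's own starting value is not used at all, apart from what z3 captures for partner number.

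The link function is a separate, lesser point. A model written for counts would be applied to bounded attitude and sex-role scores.

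**Working it through.** **1. The plan's own figure.** The only sample-size figure is for the primary outcome (11.3): m = 2(1.96 + 0.84)² × {1 + (8 − 1) × 0.01} / (8 × 0.29²) = 24.94, rounded up to 25 cohorts, or 8 × 25 = 200 men per condition. This reproduces and is not in dispute. No power figure is given for any secondary outcome. Only the 200 per condition, the design effect of 1 + 7 × 0.01 = 1.07 and, for illustration, the 0.29 effect are borrowed below.

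**2. Binary outcomes.** The right-hand side in 11.7 is β0 + β1z1 + β2t + β3z1t + γ1z2 + γ2z3 + γ3z4. Putting in the 11.6 definitions gives treatment, time, their interaction, baseline unprotected intercourse, non-monogamy and stimulant years. There is no baseline value of the outcome W, and the text allows no other reading.

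**3. Other outcomes.** The only primary-outcome model is model (1). Reusing it literally brings both its z2 and its log link. The linear model with normal errors in 11.3 is there for the sample-size calculation and is not offered as an analysis model. The log link suits partner number and outer-course frequency. The Condom Barriers Scale and BSRI scores are not counts.

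**4. What the log link does to a scale score.** The treatment effect becomes a ratio of means. Take hypothetical BSRI means of 5 and 4 on the 1–7 scoring: the ratio is 5/4 = 1.25. Score the same answers 0–6 and it is 4/3 = 1.33. The difference in means is 1 either way.

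**5. Precision, continuous scores only, assumed correlations.** In a linear model a baseline covariate with correlation r removes a share r² of the residual variance.

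- Own baseline, r = 0.5: 0.25. With r = 0.7: 0.49.
- A different variable, r = 0.1: 0.01. With r = 0.2: 0.04.

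With 200/1.07 = 187 effective men per arm and a 0.29 SD effect, power is Φ(0.29 × √(187/2) / √(1 − r²) − 1.96). This gives 0.80 to 0.82 for r = 0 to 0.2, and 0.84, 0.90 and 0.98 for r = 0.3, 0.5 and 0.7.

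**6. Chance imbalance, continuous scores only.** The standard error of a baseline difference is √(2 × 1.07/200) = 0.103 SD, so a difference of 1.96 × 0.103 = 0.20 SD is at the edge of ordinary chance. It carries r × 0.20 into the follow-up comparison: 0.10 SD at r = 0.5 and 0.14 SD at r = 0.7. Suppose z2 correlates c = 0.1 to 0.2 with the score's own baseline and predicts follow-up only through it. Adjusting for z2 then leaves r × 0.20 × (1 − c²): 0.096 to 0.099 SD and 0.134 to 0.139 SD. Almost nothing is corrected.

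**7. Is the own baseline available?** Table 3 has the Condom Barriers Scale, the BSRI and the Sexual Behavior Inventory at Visit 1. No section says which instrument records condom possession or taking clinic condoms, and the content listed in 8.3.4 names neither.

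**8. Drug use with sex.** A percentage of sexual events and a frequency are different quantities. The frequency falls if a man simply has less sex; the percentage need not. Section 8.3.4 collects a relative frequency, so counts of events with and without drugs are not shown to exist.

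**The case against.** The strongest reply is about scope. The sentence that carries the four covariates over stands in the paragraph on dichotomous outcomes. For the rest, 11.7 says only that the models are the same, and since 11.6 introduces z2 as the baseline value, an analyst could reasonably substitute each outcome's own baseline. That stands as a possible reading. It is not written, though, and the explicit carry-over for the binary outcomes points the other way. A reader might infer that the protocol explicitly imposes the wrong baseline on all seven outcomes; the text supports this only for two.

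Other parts of the reply also stand.

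- For partner number, z3 is itself a dichotomised baseline partner measure, so some own-baseline information is already in the model.
- A log-link GEE on a strictly positive mean is valid. The objection to it is interpretation, not error.
- Cohort randomisation adds little: √1.07 = 1.03, about 3% on the standard error of a baseline difference, and allocation is blocked within site.
- The r² arithmetic belongs to linear models. In a logistic model, covariate adjustment does not remove residual variance in this way, and it changes the odds ratio being estimated. No gain can be quoted for the two outcomes where the mismatch is explicit.
- Baseline data for those two outcomes are not documented. Drug-free clinics are asked to recruit men as they enrol (5.1), so earlier taking of clinic condoms may tell little for about half the sample (280 of 560).

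**Conclusion.** The point holds in limited form. For the two dichotomous outcomes, 11.7 plainly adjusts for another outcome's baseline, against the rationale in 11.6. For the others, the literal wording implies the same covariate and gives the Condom Barriers Scale and BSRI scores a log link that is valid but ill-suited. The two descriptions of drug use with sex do not agree.

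A reader might conclude that the secondary treatment effects would be biased, or that a fixed number of participants is being thrown away. The documents support neither. Randomisation still protects against systematic bias; what is lost is precision and correction of chance imbalance, on secondary outcomes with no stated power target. The 25% to 49% reduction in residual variance applies to the continuous scores only and rests on assumed correlations of 0.5 to 0.7. The sample size is unaffected. The change is worth making because it costs almost nothing.

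**What to change.** In section 11.7:

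1. Define z2 as the baseline value of the outcome being analysed, for both groups of outcomes, wherever Visit 1 collects it. Baseline unprotected acts may stay as an optional extra covariate.
2. Confirm which instrument records condom possession and taking clinic condoms, and whether it does so at Visit 1. If a baseline value does not exist, say so and state the covariates used instead.
3. State an identity link for the Condom Barriers Scale and BSRI scores, and keep the log link for counts and the logit for the two binary outcomes.
4. Use one definition of drug use with sex in 11.2 and 11.7, chosen to match what the inventory records. No particular model need be prescribed until that is settled.

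The cost is a few sentences and minor programming. No new data are needed for the Condom Barriers Scale, the BSRI or items in the Sexual Behavior Inventory, and the sample size does not change.
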